#### Primary estimand

The primary interest is to estimate the relative bioavailability, measured by Cmax and AUC(0-inf), following a **CCI** of bepirovirsen via PFS SSD versus a vial in healthy adult participants.

The primary PK estimands are described by the following attributes:

- Population:
 

Healthy male and female participants aged 18 to 55 years.
- Treatment Condition:
 

**CCI** of bepirovirsen injection administered via PFS SSD versus **CCI** of bepirovirsen administered via a vial.

**CONFIDENTIAL**219239  
Protocol

- Variables:

AUC(0-inf) and Cmax.

- Summary measure:

Ratio of geometric means of PFS SSD versus vials for Cmax and AUC(0-inf).

- Intercurrent Events:

Use of prohibited medication. This intercurrent event is not expected to impact the PK of bepirovirsen so a treatment policy strategy will be used, and the individual PK concentrations after the occurrence of the intercurrent event will still be included in the PK analysis.

Participants who did not receive **CCI** the injections and had an incomplete or erroneous dosing. A principal stratum strategy policy will be used, where the strata of interest is the group of participants who are able to receive the complete dose.

A supplemental estimand will also be analyzed as per the primary estimand, except for the intercurrent event of incomplete dosing will use a treatment policy strategy.

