### **9.2. Analysis sets**

Analysis Set	Definition / Criteria	Analyses Evaluated
Screened	

• All participants who were screened for eligibility.

	

• Study Population

CONFIDENTIAL

219239  
Protocol

Analysis Set	Definition / Criteria	Analyses Evaluated
Enrolled	
 
• All participants who entered the study (who were randomized or received study intervention or underwent a post screening study procedure).
 
• Note screening failures (who never passed screening even if rescreened) and participants screened but never enrolled into the study (Met eligibility but not needed) are excluded from the Enrolled analysis set as they did not enter the study.
 
	
 
• Study Population
 

Randomized	
 
• All participants who were randomly assigned to study intervention in the study.
 
	
 
• Study Population
 

Safety	
 
• Participants who received study intervention
 
• Participants will be analyzed according to the study intervention administered.
 
	
 
• Safety
 

PK concentration	
 
• All participants in the Safety analysis who received CCI [REDACTED] the injections and had at least 1 non-missing PK assessment (NQ values will be considered as non-missing values).
 
• Data will be reported according to the actual study intervention.
 
	
 
• PK concentration
 

PK Parameter	
 
• All participants in the PK concentration population for whom valid and evaluable plasma PK parameters are derived. This primary analysis population will be used in the assessment and characterization of PK parameters (summary and analysis tables and figures).
 
	
 
• PK parameter
 

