3. ANALYSIS SETS

Analysis Set	Definition / Criteria	Analyses Evaluated
Screened	
 • All participants who were screened for eligibility. 	
 • Study Population
Enrolled	
 • All participants who entered the study (who were randomized or received study intervention or underwent a post-screening procedure). • NOTE: screening failures (who never passed screening even if rescreened) and participants screened but never enrolled into the study (Met eligibility but not needed) are excluded from the Enrolled Analysis set as they did not enter the study. 	
 • Study Population
Randomised	
 • All participants who were randomly assigned to study intervention in the study. 	
 • Study Population
Safety	
 • Participants who received study intervention • Participants will be analysed according to the study intervention administered. 	
 • Safety
PK concentration	
 • All participants in the Safety analysis who received CCI [REDACTED] the injections and had at least 1 non-missing PK assessment (NQ values will be considered as non-missing values). • Data will be reported according to the actual study intervention. 	
 • PK concentration
PK Parameter	
 • All participants in the PK concentration population for whom valid and evaluable plasma PK parameters are derived. This primary analysis population will be used in the assessment and characterization of PK parameters (summary and analysis tables and figures). 	
 • PK parameter

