4. STATISTICAL ANALYSES

4.1. General Considerations

4.1.1. General Methodology

The Safety analysis set will be used for all study population analyses and safety analyses, unless otherwise specified. The PK analysis set will be used for PK analyses. Study population and safety tables will be displayed overall and by randomised groups.

Any subjects randomised in error to the incorrect weight strata will be summarised based on the actual stratum per data collected in the CRF.

Confidence intervals will use 90% confidence levels unless otherwise specified.

Unless otherwise specified, continuous data will be summarized using descriptive statistics: n, mean, standard deviation (std), median, minimum, and maximum.

Categorical data will be summarized as the number and percentage of participants in each category.

Blood sampling time will be related to the start of dosing. Linear and semi-logarithmic individual plasma concentration-time profiles (by randomized groups and by subject) and mean (\pm SD) and median profiles will be plotted for each randomized group. Plasma concentrations of bepirovirsen will be listed and summarised by randomized groups and nominal time. Summaries, including mean (\pm SD) and median profile plots, will also be produced by randomized group and injection site; and randomized group and baseline body weight category (CCI [REDACTED]); and randomized group, injection site and baseline body weight category (CCI [REDACTED]).

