4.2.3. Supplemental estimands

A supplemental estimand to the primary objective assessing the impact of participants who were unable to take the complete dose. The estimand will be the same as the primary estimand except for the intercurrent event of incomplete dosing (participants who did not take CCI vials) which will now be considered using a treatment policy strategy.

CCI

CCI

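### Do the treatment-policy supplemental PK analyses lack an analysis population of their own?

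*SAP*

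**What the plan says.** Protocol Section 3 handles incomplete or erroneous dosing in the primary estimand by a principal stratum strategy, in which "the strata of interest is the group of participants who are able to receive the complete dose". The secondary estimands do the same. Each has a supplemental version that changes only the strategy for incomplete dosing, to treatment policy.

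The SAP repeats this. Section 4.2.3 changes the handling of "the intercurrent event of incomplete dosing (participants who did not take CCI vials) which will now be considered using a treatment policy strategy" (the number of vials is redacted). Section 4.3.1.4 refers back to 4.2.3 for the secondary objectives.

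On populations, SAP 4.1.1 states: "The PK analysis set will be used for PK analyses". No set of that name is in the Section 3 table. The table has these sets:

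- Safety: "Participants who received study intervention".
- PK concentration: "All participants in the Safety analysis who received CCI [REDACTED] the injections and had at least 1 non-missing PK assessment".
- PK Parameter: "All participants in the PK concentration population for whom valid and evaluable plasma PK parameters are derived". The entry adds: "This primary analysis population will be used in the assessment and characterization of PK parameters".

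Protocol 9.2 has the same table, with the same black-out before "the injections and had at least 1 non-missing PK assessment".

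**The concern.** A principal stratum of completely dosed participants and a treatment-policy comparison that keeps the incompletely dosed need different groups of people. Yet PK Parameter is nested in PK concentration, so both pass through one injection condition, and 4.1.1 names only one set, under a label that does not exist. No readable sentence says which set the supplemental estimands use.

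At stake is the one planned check on the complete-dose restriction. It matters most for Groups 3 and 4, where a partial injection can be a consequence of self-administration, the very thing being compared. If main and supplemental analyses ran on the same people, they would agree exactly, and a reader could take that agreement as reassurance when nothing had been tested.

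Two wording points add to the impression. Section 4.2.3 describes the event in terms of vials, although Groups 2 to 4 use the PFS SSD (protocol 8.4.8). And the main intercurrent event covers incomplete or erroneous dosing, while the supplemental text mentions only incomplete dosing.

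**Working it through.** The plan gives no figure to reproduce: group sizes, number of injections, variability and precision are all redacted. The check is a reading of the text, with a small illustration of size.

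**1. Do the main analyses have a set?** Yes. SAP Section 3 and protocol 9.2 both make PK Parameter the primary population for PK parameter summaries and analyses. Cmax and AUC(0-inf) are those parameters. The loose label in 4.1.1 therefore leaves no doubt about where the main analysis starts.

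**2. What follows under each reading of the redacted qualifier?**

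| Qualifier | Main estimands | Supplemental estimands |
|---|---|---|
| All injections | PK Parameter is already the completely dosed group | Incompletely dosed participants must be added from the Safety set |
| At least one injection | PK Parameter must be cut to the completely dosed, which the protocol's principal stratum wording requires | PK Parameter can be used as it stands |

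Under the second reading nothing is missing. Under the first, the analyst must look beyond the Section 3 PK sets, but 4.2.3 and 4.3.1.4 give the reason: they exist to assess the impact of participants who could not take the whole dose. That purpose cannot be met by leaving those participants out. The data should exist, since protocol 8.5 ties PK sampling to the schedule of activities with no readable condition on complete dosing.

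The readable text leans towards *all*. The protocol's intercurrent event refers to the injections in matching terms, the Safety set already requires receipt of study intervention, and PK Parameter is called the primary population. This is a leaning only.

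**3. Where would a supplemental population be named?** Normally in SAP 4.2.1 to 4.2.2, beside 4.2.3, or in 4.3.1.1 to 4.3.1.2. All of these are redacted or not shown. SAP Section 1 also places data-handling detail and display specifications in the Output and Programming Specification, which is not public.

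**4. How large could the effect be?** Assume a true ratio of 1, dose-proportional exposure, and shares *p1* and *p2* of the two arms receiving fraction *d* of the dose. Then log ratio = (*p1* − *p2*) × ln(*d*), so the ratio is *d*^(*p1* − *p2*). Every *p* and *d* is assumed.

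| *p1* (*p2* = 0) | *d* = 0.5 | *d* = 0.75 |
|---|---|---|
| 2% | 0.5^0.02 = 0.986 | 0.75^0.02 = 0.994 |
| 5% | 0.5^0.05 = 0.966 | 0.75^0.05 = 0.986 |
| 10% | 0.5^0.10 = 0.933 | 0.75^0.10 = 0.972 |

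With 10% against 2%, the exponent is 0.08 and the ratios are 0.946 and 0.977. With no incomplete dosing, or equal rates in both arms, the shift is nil. On one shared set, the supplemental ratio would differ from the main one by 0 in every row.

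For scale, SAP Section 2 shows a reference range starting at 0.8. If that is read as a lower bound for the ratio (the compared quantity is redacted), the shift alone reaches it at *p1* = ln(0.8)/ln(0.5) = 0.322 or ln(0.8)/ln(0.75) = 0.776, that is, 32% or 78% of one arm incompletely dosed.

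**5. The wording points.** Vials appears in a parenthesis next to a redaction, and 4.3.1.4 itself speaks of the complete dose, which covers either presentation. Incomplete dosing reads naturally as shorthand for the protocol's combined event. Read narrowly, erroneous dosing simply keeps the main strategy, because the supplemental estimand is otherwise the same as the main one. Neither reading is shown to alter a result.

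**The case for a change.** The best case for a change is structural. Whatever the hidden word is, one set used without further restriction cannot serve both kinds of estimand. If the word is *all*, any redacted text naming a supplemental population must reach outside the Section 3 PK sets, so that table would still be incomplete. The remedy is cheap: some wording, at most one more set, and no new data. The self-administration arms, one of them untrained, are where the check could be informative.

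Part of this stands. The label in 4.1.1 is undefined, no readable text names a set for the supplemental estimands, and vials does not fit the PFS SSD groups. What does not stand is the step to a faulty analysis. It needs the hidden word to be *all*, every redacted passage and the programming specification to be silent, and an analyst to let one general sentence in 4.1.1 override the specific instruction in 4.2.3. The first two conditions cannot be shown from the public text, and the third is not how a competent team reads an SAP. Dosing also takes place at the site, given by staff or under medical supervision (protocol 6.5), and no failure rate is given that would make a material number of incomplete doses likely.

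**Conclusion.** No change to the plan is called for. This is a clerical label plus a detail that analysts would fill sensibly: the estimands state who belongs in each analysis, and SAP 4.7 reports no departure from the protocol's planned analysis, so the protocol's two strategies carry over.

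Any effect is confined to the supplemental analyses. Under the assumptions above, the supplemental ratio would move by between 0.6% (0.994) and 6.7% (0.933) for 2% to 10% incomplete dosing in one arm, and by nothing if all doses are complete or the rates are equal. No primary or secondary result is shown to be wrong, and the study estimates ratios without formal tests (SAP 2.1).

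The conclusion rests on reading 4.2.3 as the specific rule that governs the general sentence in 4.1.1, and on not counting redacted text as absent. It would need another look only if the unredacted plan were found to require all injections for every PK analysis, the supplemental ones included.

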4.3.1.3. Sensitivity analyses

If large differences in exposure due to injection site in our primary endpoint analysis are observed, then a sensitivity analysis exploring injection site differences will be conducted

only for the secondary objectives using fixed effect models as specified in Section 4.3.1.2 and will be analysed and reported in a similar manner as described in Section 4.2.2. This analysis will only include those subjects from randomised group 2 where the injection site is thigh or abdomen.

4.3.1.4. Supplemental estimands

[figure not shown]
A supplemental estimand to the secondary objective assessing the impact of participants who were unable to take the complete dose will be considered as described in Section 4.2.3.

4.4. Exploratory Analyses

CCl

CCl

CCI

4.4.3. Pharmacodynamic Effect of Bepirovirsen (Biomarker Analysis)

Additional details of the biomarker analysis will be provided in the biomarker analysis plan and the results will be documented in a separate report.

4.5. Safety Analyses

The safety analyses will be based on the Safety Analysis Set, unless otherwise specified.

4.5.1. Adverse Events

An AE is considered treatment emergent (TEAE) if the AE onset date is on or after treatment start date. An AE is serious (SAE) if it results in death, is life threatening, requires inpatient hospitalization or prolongation of existing hospitalization, results in persistent or significant disability/incapacity, is a congenital anomaly/birth defect or in other situations described in Section 10.3 Appendix 3 of the protocol.

If AE start date is completely missing and the end date is on or after the treatment start date, the AE will be assumed to be treatment emergent. All AE summaries will be based on treatment emergent events unless otherwise specified.

Adverse events will be coded using the latest version of Medical Dictionary for Regulatory Affairs (MedDRA) coding dictionary, to give a Preferred Term (PT) and a System Organ Class (SOC). These PTs and SOCs will be used when summarising the data. The severity of AEs and SAEs will be determined by the investigator according to the Division of AIDS (DAIDS) grading system Version 2.1 [National Institute of Allergy and Infectious Diseases. Division of AIDS, 2017], unless specified otherwise in the protocol.

For AEs by maximum grade summary tables, if a participant reports an AE more than once within an SOC/PT, the AE with the most severe intensity will be included in summaries. Relationship to study treatment, as indicated by the investigator, is classified as “not related” or “related”. Adverse events with a missing relationship to study treatment will be regarded as “related” to study treatment.

The following table AE summaries will be presented for each randomized group:

1. AEs overview: summary of the number and percentage of participants with any adverse event, AEs related to study treatment, any SAEs, SAEs related to study treatment, fatal SAEs and fatal SAEs related to study treatment.
2. All AEs by SOC and PT.
3. All AEs by SOC and PT and maximum grade.
4. All treatment-related AEs by SOC and PT.
5. All treatment-related AEs by SOC and PT and maximum grade.
6. SAEs by SOC and PT.
7. Treatment-related SAEs by SOC and PT.
8. AEs leading to withdrawal from the study by SOC and PT.
9. AEs leading to withdrawal from the study by overall frequency.
10. Fatal AEs by SOC and PT.
11. Serious AEs by SOC and PT (number of participants and occurrences).
12. Serious Fatal and Non-Fatal Treatment-Related AEs by overall frequency.

Number of participants with AEs will be summarized if it is not specified otherwise.

In summary tables where AEs are presented by SOC, PT, and maximum grade, SOCs will be sorted in descending order of the total incidence then alphabetically, PTs will be sorted in descending order of the total incidence then alphabetically within the SOC.

Deaths will be summarized and listed including primary cause of death.

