Injection site reactions	
ISRs have been reported with ASOs and reported in clinical studies with bepirovirsen. ISRs were the most common study treatment-related AEs with the majority reported as Grade 1 severity (mild). The majority of ISRs are reported as injection site erythema, injection site pain and injection site pruritus. Few events have led to treatment discontinuation.
	
Evaluations: Participants are assessed for ISRs at all visits as per the SoA.

CONFIDENTIAL

219239  
Protocol

Potential Risk of Clinical Significance	Summary of Data/Rationale for Risk	Mitigation Strategy
Study Procedures		
Blood drawn	Risks with phlebotomy include bruising, bleeding, infection, and nerve damage.	Procedures to be performed by trained personnel (i.e., study nurse).
Handling and usage risks associated with PFS SSD	The IMP will be administered by or under the supervision of health care professionals. Anticipated device effects are nonserious, effects are unlikely, improbable, occasional, or remote and any effects are due to user errors.	Instructions for use on how to handle and use the devices will be provided.

**CONFIDENTIAL**219239  
Protocol**2.3.2. Benefit assessment**

As this Phase 1 study will be conducted in healthy adult participants, there will be no direct benefit to study participants included in this study.

Participants in this study will contribute to the development of an improved delivery of treatment for patients with CHB.

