#### **4.2. Scientific rationale for study design**

Conducting the study in healthy participants mitigates the recruitment and patient burden limitations with administering a single dose of bepirovirsen to CHB patients. A population of healthy participants is frequently used in the assessment of the relative bioavailability of both small and large molecules. In addition, healthy participants are a suitable population for biopharmaceutical PK comparability studies, and the data can be extrapolated to other populations. In addition, usability of the PFS SSD can be reliably assessed in healthy participants via questionnaires to support design of the human factors summative evaluation.

[REDACTED]

[REDACTED]

[REDACTED].

Bepirovirsen has a half-life of approximately [REDACTED] in healthy subjects. A [REDACTED]

[REDACTED]

[REDACTED]

[REDACTED]

[REDACTED]

**CONFIDENTIAL**219239  
Protocol

A [cci] dose of bepirovirsen will be administered as [cci] injections at 1 of 3 injection sites (upper arm, abdomen, or thigh) when administered by an HCP, or at 1 of 2 injections sites (abdomen or thigh) when self-administered. Upper arm is not a feasible administration site for self-administration. To prevent bias and maintain balance in treatment groups, the injection site will be randomized in addition to the randomization for device. To minimize the impact of potential confounding factors and variability, the randomization will also be stratified by body weight as this has been associated with bepirovirsen exposure.

Collection of PK blood samples up to Day [cci] will ensure that the bepirovirsen plasma concentration-time profile is well described with the extrapolated portion of AUC(0-inf) below [cci].

The study will be open-label. This is acceptable because the primary and secondary endpoints are PK parameters, which are not subjective measures. Any potential for selection bias will be reduced by central randomization.

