1.2. Study Design

Overview of Study Design and Key Features	
Design Features	
This is a Phase 1, open-label, randomized study to investigate SC bepirovirsen when delivered via SC injection from a vial and PFS SSD in healthy adult participants. The study will assess relative bioavailability, safety, and tolerability, as well as the usability of the PFS SSD for self-administration.
 
A total of approximately CCI participants will each complete a single study session, in a parallel design, and will take up to CCI weeks to complete the study.
 
Participants will be screened within 28 days before dosing. They will attend the clinical unit the day before dosing (Day -1) and will remain inpatient until 2 days after dosing (Day 3). Participants will return for outpatient visits on Days CCI
 
Blood samples will be taken to measure levels of bepirovirsen and ADAs against bepirovirsen, and safety and tolerability will be assessed from before dosing and until the final visit. The observing HCP and participants in Groups 3 and 4 will complete questionnaires, respectively, during and after dosing, to assess usability of the PFS SSD for self-administration. Blood samples will also be taken for biomarker analysis before dosing and up to 48h after dosing.

Study intervention	CCI

Overview of Study Design and Key Features	
	CCI
Study intervention Assignment	Participants will be randomized in a ratio of 3:3:2:2 to one of the four treatment groups. The randomization will be stratified by body weight (CCI [REDACTED]). The site of injection will be randomized in a 1:1:1 ratio to upper arm, abdomen, and thigh in Groups 1 and 2, and in a 1:1 ratio to abdomen or thigh in Groups 3 and 4.
Interim Analysis	CCI

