4.5.1.1. Adverse Events of Special Interest

The following AEs of special interest (AESI) will be reported to characterise the important potential risks (safety concerns) for bepirovirsen:

- ALT increase.
- Vascular inflammation and complement activation.
- Thrombocytopenia.
- Renal injury.
- Injection Site Reactions.

In addition, the following AEs which are identified as significant events but not as safety concerns will be reported:

- Immune-mediated events
- Neutropenia

An up-to-date list of standardized MedDRA Queries (SMQ)s, high level terms (HLTs) or individual PTs used to identify AESIs is periodically updated and stored in a central location. At the time of Database Lock (DBL), the latest version of the terms will be extracted and used to identify AESIs.

All AESIs and significant events will be summarized by SOC and PT, and summarized by SOC, PT, and maximum grade. Serious AESIs will be summarized by SOC and PT. All AESIs and significant events will be listed. Also, a listing of non-fatal SAEs will be produced.

Separate outputs will be created for each AESI and significant event category (ALT increase, vascular inflammation and complement activation, thrombocytopenia, renal injury, immune-mediated events, neutropenia, and injection site reactions) to explore the data in more detail if data permits.

Event Characteristics: The characteristics of all event occurrences during the post-baseline period will be summarized, which looks at event characteristics (serious, resulting in hospitalisation, drug-related, leading to withdrawal, maximum intensity, or maximum grade, fatal), number of events per participant, outcome, maximum grade or intensity and action taken. Event characteristics will be described by the proportion based on all subjects and the proportion based on subjects with the event for each of these items.

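### Injection-site reactions are planned by randomised group without a split by site, so the descriptive Group 2 versus Group 3 or 4 comparison would carry one third of any upper-arm versus thigh/abdomen difference

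*SAP*

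**What the plan says.** **Allocation.** SAP 1.2 states "Participants will be randomized in a ratio of 3:3:2:2 to one of the four treatment groups". On site it says: "The site of injection will be randomized in a 1:1:1 ratio to upper arm, abdomen, and thigh in Groups 1 and 2". The self-injection groups, 3 and 4, are split equally between two sites only, with no upper-arm injections. Protocol 4.2 gives the reason for the different site lists: "Upper arm is not a feasible administration site for self-administration". Protocol 8.4.8 shows that the prefilled syringe with safety device (PFS SSD) is used in Groups 2 to 4, which leaves Group 1 as the vial group.

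**Safety displays.** The safety objective (Protocol 3, SAP 1.1) is a comparison of safety and tolerability by randomised group. SAP 4.1.1 has safety tables shown overall and by randomised group. SAP 4.5.1 opens its list of AE tables with "The following table AE summaries will be presented for each randomized group". SAP 4.5.1.1 includes ISRs among the adverse events of special interest (AESIs) and says "All AESIs and significant events will be summarized by SOC and PT, and summarized by SOC, PT, and maximum grade". It also provides a separate output for each AESI category if the data permit. Its list of event characteristics does not include injection site.

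**Contrast with PK.** SAP 4.1.1 says that PK concentration summaries "will also be produced by randomized group and injection site". SAP 4.3.1.3 describes a PK sensitivity analysis for the secondary objectives, run if large site differences in exposure are seen, in which Group 2 is limited to participants injected in the thigh or abdomen.

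**The concern.** Protocol Table 4 reports ISRs as the most common treatment-related adverse events with bepirovirsen, mostly mild. They are local events, and the trial randomises where the injection goes. Readers will use the by-group ISR table to judge whether self-injection is tolerated as well as injection by a professional, because the programme's stated aim includes eventual self-administration (Protocol 2.2).

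That table sets a three-site group beside two-site groups. The imbalance is fixed by the design, so randomisation does not even it out. Were upper-arm ISR rates different from those at thigh and abdomen, part of the Group 2 versus Group 3 or 4 difference would reflect site and not who injected. It could create an apparent effect of self-injection or hide a real one. The plan already handles this imbalance for PK but has no matching provision in the readable safety text.

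**Working it through.** **1. Inputs.** The allocation of 3:3:2:2 and the site ratios come from SAP 1.2 and Protocol Table 6. ISR rates by site are not given, so they are assumed below. Group sizes are redacted, so shares are used.

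**2. Reproducing the plan's own statement.** The ratio has 3 + 3 + 2 + 2 = 10 units.
- Groups 1 and 2: 3/10 each over three sites, so 1/10 of all randomised per site.
- Groups 3 and 4: 2/10 each over two sites, so 1/10 per site.
- Thigh plus abdomen: 2 units in every group.

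This agrees with the statement in the sample-size text of both documents that Groups 3 and 4 match Groups 1 and 2 in numbers at the applicable sites. The upper-arm share is 1/3 in Groups 1 and 2, and 0 in Groups 3 and 4.

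**3. Site component of the crude contrast.** Let p_a be the upper-arm ISR rate and p_o the mean of the thigh and abdomen rates (1:1 in every group). Suppose that who injects has no effect.
- Expected Group 2 rate: (p_a + 2p_o)/3
- Expected Group 3 or 4 rate: p_o
- Group 2 minus Group 3 or 4: (p_a + 2p_o)/3 - p_o = (p_a - p_o)/3

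| Assumed p_a - p_o (points) | Site component, Group 2 minus Group 3/4 (points) |
|---|---|
| -20 | -6.7 |
| -10 | -3.3 |
| 0 | 0 |
| +10 | +3.3 |
| +20 | +6.7 |
| +30 | +10.0 |

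The result depends only on the site difference, not on the level of p_o.

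**4. Masking example, with assumed rates.** Take 30% at thigh/abdomen, 60% at upper arm, and a true excess of 10 points from self-injection.
- Group 2: (60 + 30 + 30)/3 = 40%.
- Group 3 or 4: 30 + 10 = 40%.
- The by-group table shows no difference. With Group 2 limited to thigh and abdomen it shows 40 - 30 = 10 points.

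**5. Group 1 versus Group 2.** Both have the 1:1:1 mix, so the expected site component is zero.

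**6. Price of the restriction.** With equal variances, the crude contrast has variance proportional to 1/3 + 1/2 = 5/6. The restricted contrast has 1/2 + 1/2 = 1. The standard error ratio is the square root of 1/(5/6), or 1.095, so about 10% larger. The expected site component falls to zero.

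**The case against.** The strongest reply is that nothing in the documents says ISRs depend on site. Protocol Table 4 describes reaction types and severity only, and Protocol 4.2 links exposure to body weight. This stands: site dependence is an assumption, its sign is open, and the distortion may be zero. With group sizes redacted, no one can say whether a few points would show above sampling error.

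A second reply is that the safety comparison is descriptive. The documents test no formal hypotheses (Protocol 9.1.1, SAP 2.1), and the professional-versus-self objectives concern PK. This also stands and limits the weight of the point. It does not remove it, since the safety objective is itself a comparison by group and the table will be read that way.

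A third reply is that a site split may exist elsewhere. SAP 1 defers display specifications to the Output and Programming Specification, SAP 4.5.1.1 allows further AESI output, and parts of both documents are blacked out. The point is therefore about readable text. However, the AE and AESI text is legible, the extra output is conditional, and neither provision names site.

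A reader might infer that the device comparison is distorted too. The documents do not support that. Groups 2, 3 and 4 all use the PFS SSD, so Group 2 versus 3 or 4 contains no device contrast, and the device contrast (Group 1 versus 2) has the same site mix on both sides.

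**Conclusion.** The point holds as a cheap improvement. In the readable text, ISRs are shown by randomised group with no split by site, while the upper-arm share is one third in Group 2 and zero in Groups 3 and 4. The crude Group 2 minus Group 3 or 4 ISR difference therefore contains one third of any upper-arm versus thigh/abdomen difference, in either direction. Over the assumed range in the working this is about -6.7 to +10 points.

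The size rests wholly on assumed site differences and cannot be narrowed from the documents. It would be wrong to conclude that the ISR comparison is known to be biased, or that the primary PK result is affected. The finding concerns how one descriptive safety table can be interpreted.

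**What to change.** Keep the planned by-group tables. Add to SAP 4.5.1.1 one ISR table giving incidence and maximum grade by randomised group and randomised injection site. State that Group 2 versus Groups 3 and 4 is to be read from the thigh and abdomen rows, in line with the Group 2 restriction in SAP 4.3.1.3. Leave Group 1 versus Group 2 on all three sites.

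The cost is one table shell and no new data, since site is already a randomised factor. There are two drawbacks: each group-by-site cell holds only one tenth of those randomised, and setting aside the upper-arm third of Group 2 raises the standard error of the contrast by about 10%. Retaining the by-group table beside the new one lets the reader see both.
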